5. EXPECTED ADVERSE EVENTS/DOSE MODIFICATIONS

5.1 Expected Adverse Events Associated with M032

Although M032 has not yet been used in humans, the adverse events it might produce are expected to be similar to the adverse events observed in the Phase I trials of a similar genetically-engineered herpes simplex virus, G207. G207 caused no DLT and the adverse events that were observed following treatment were not thought to be attributable to the study drug.

Adverse events occurring after the administration of G207 included the following, which are therefore expected to possibly occur following M032:

- | | | |
|--------------------|------------------------------|---------------------------------|
| • asthenia | • hemiplegia | • dysphasia |
| • amnesia | • confusion | • depression |
| • nausea | • headache | • deep vein thrombosis |
| • somnolence | • decreased consciousness | • seizure |
| • leukopenia | • anemia | • abnormal erythrocytes |
| • peripheral edema | • cachexia | • urinary tract infection |
| • fever | • varicella zoster infection | • tumor progression |
| • pneumonia | • abnormal mentation | • increased liver transaminases |
| • death | • stroke | • pseudoprogression |

Other adverse events that might be expected based on the origin of M032 and on the patients' disease include the following:

- hematoma
- encephalitis
- hepatitis
- disseminated HSV infection
- allergic response to M032
- nuchal rigidity
- photophobia
- autoimmune response to CNS tissues

Any of the above adverse events will be considered a DLT, if possibly, probably or definitely attributable to M032 and if the severity of the adverse event is Grade 3 (in some situations) or Grade 4, as defined in **Section 4.2**.

Subjects will be observed closely for evidence of any adverse events. After the delivery of M032, subjects will be observed in a Clinical Research Unit bed, a step down unit or the Neurosurgical ICU per the discretion of the surgeon. The subjects' vital signs (temperature, blood pressure, pulse, respiratory rate) and neurologic function and limited neurological exam will be monitored every hour for the first twelve hours, then every two hours for the next 12 hours, then every 4 hours for the next 24 hours. Thereafter, the frequency of monitoring will be determined by the attending physician(s) based on the medical condition of the patient.

After discharge the subject will continue to be closely followed for evidence of adverse events, with outpatient follow-up evaluations scheduled at Day 10 and Months 1, 2, 3, 4, 5, 6, 9 and 12, or more often if

medically indicated. HSV detection will be performed at additional time points. The visits at months 2, 4 and 5 will consist of sample collections and a study coordinator visit only. Due to the complicated procedure for obtaining samples remotely at visits 2, 4 and 5, if a patient is unable to travel then, and if determined feasible by the PI, an attempt can be made to have the specimens collected by the patients' referring physician and sent to UAB for analysis.

The safety evaluation schedule is outlined in detail below in Section 8. Per FDA guidelines, subjects will be followed for survival. This will be achieved with monthly phone calls to subject. Additionally, when possible, subjects will be followed for emergence of any chronic or acute conditions that might be attributed to the study agent for up to 15 years during clinical visits with their standard of care practitioner.

Most adverse events will be managed according to standard conventions. General or specific neurologic worsening observed in the first several days after M032 administration could be due to edema, hydrocephalus, hematoma, or encephalitis. Such problems occurring later may also be attributable to tumor progression. When appropriate, an MRI will be done to help determine the cause of the neurologic changes.

- Cerebral edema/hydrocephalus: This commonly occurs in tumor patients post-operatively, and usually responds to standard measures for the treatment of increased intracranial pressure.
- Hematoma: PT, PTT, and platelet count will be obtained. A small hematoma may simply be watched and the patient treated as above for edema and then rescanned to exclude an enlarging lesion. A large hematoma or one associated with progressive neurologic deterioration may require operative evacuation.
- Encephalitis: Post-operative fever is not uncommon. However, fever $>102^{\circ}\text{F}$ (with or without seizures) extending in duration >48 hours, in the presence of a waning Glasgow Coma Scale and an increase in the area of hemorrhagic necrosis extending beyond the borders of the tumor on MRI are suggestive of viral encephalitis. If, in the opinion of the PI, it is safe and indicated, a cerebrospinal fluid sample will be obtained and analyzed by polymerase chain reaction (PCR) for evidence of HSV-1. Otherwise, or if CSF results are not diagnostic, a stereotactic biopsy will be considered. This biopsy will be taken to assess for presence of M032 or wild-type HSV-1, as well as for histopathologic evidence of encephalitis. This will consist of a minimum of 2-3 needle core biopsies that will undergo standard hematoxylin and eosin (H&E) staining as well as immunostaining for HSV-1, leukocyte common antigen, glial fibrillary acidic protein (GFAP), and IL-12 immunostaining if possible. High-dose antiviral therapy with intravenous acyclovir may be implemented in consultation with the Medical Monitor, [name], and will be administered according to established method [37].
- Disseminated HSV Infection: Disseminated multi-organ disease attributed to HSV is exceedingly uncommon, even in the immunocompromised host. Such disease has been encountered in the newborn with disease identified as 'disseminated multiorgan involvement' and occurs in about 25% of newborns with this disease (incidence 1:10,000 deliveries).[38] In adults, disseminated disease has been encountered in stem cell transplant recipients and, very rarely, pregnant women.[39] In all circumstances, disseminated disease is associated with a systemic host response of fever, and findings compatible with sepsis, including hepatic dysfunction. To monitor for these rare events, most importantly, serial physical examinations will be performed to assess for fever and symptoms of sepsis or hepatic dysfunction. In addition, serial blood specimens will be obtained at Days 2, 10, 28 and monthly thereafter and cultured for infectious HSV. Any positive cultures will be analyzed by PCR to discriminate between wild type HSV-1 and mutant M032 HSV. Should a patient develop fever, rash, or unexplained elevations in liver function tests in conjunction with a concomitant increase of infectious HSV by plaque assay in blood specimens (exceeding prior values by 2 logs), patients will undergo a 21 day course of treatment with acyclovir for presumed disseminated HSV infection. Parenthetically, it should be noted that oncolytic HSV therapy for metastatic colon carcinoma involving the liver led to detectable HSV DNA in the blood but in the ABSENCE of clinical symptomatology[40]; thus, increasing levels as well as fever will both be required to therapeutically intervene. Should 2 Grade 3 or 4 toxicities attributable to disseminated HSV infection occur in the same dose level, the prior dose level shall be declared the MTD and enrollment will be halted.

- **Cytokine storm:** although unlikely, this would not be entirely unexpected. Management of cytokine storm will focus on the pathology and symptoms. Anti-inflammatory agents (for example corticosteroids) can minimize the cytokine response decreasing morbidity and mortality. Should a cytokine storm or related toxicity occur, we will utilize antiviral therapy active against HSV (eg acyclovir) in combination with immunomodulatory agents to interrupt HSV replication and IL-12 production and effects, thereby reducing and/or eliminating morbidity and mortality. Close observation of the subject for 24 hours after the crisis will be implemented (vital signs q hour, respiratory and cardiovascular support as needed, fluid maintenance as needed).

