4.2 Definition of Dose-Limiting Toxicity

The Cancer Therapy Evaluation Program (CTEP) has published Common Terminology Criteria for Adverse Events, version 4.0 for the grading of adverse events experienced in clinical trials for anti-neoplastic agents. Any grade 3 or greater non hematologic toxicity as defined by NCI CTCAE v 4, and considered as being possibly, probably or likely related to M032 will be considered a Dose Limiting Toxicity (DLT). However, specific symptoms including seizures, neurologic deficits such as weakness, dysphasia or sensory loss are prominent in this patient population due to the fact that these tumors frequently disrupt the function of normal areas of eloquent brain. Neurologic symptoms from involvement of eloquent brain are commonplace; corticosteroid, radiation, and chemotherapies also produce pre-existing symptoms in almost all cases. The pre-existing conditions listed in the **Table** on the following page are acceptable for inclusion in the clinical trial, provided the subjects meet the other inclusion and exclusion criteria.

For all of these pre-existing conditions, DLTs will be defined as progressive involvement of neurological dysfunction not attributable to tumor progression and/or the development of life threatening symptomatology associated with the original baseline status.

Neurologic deterioration will not be considered dose-limiting if it resolves back to the patient's baseline within two weeks of completing treatment. For example, increased weakness or aphasia that occurs during the infusion will be treated with increasing steroid doses and/or slowing of infusion rates, but not treated as a DLT if symptoms improve to baseline within fourteen days of completing treatment. Because of the site of M032 inoculation, important additional events that will be considered dose-limiting toxicities if they are likely related to M032 include death, stroke, hematoma requiring surgery, untreatable neurologic deterioration, unresponsive systemic infection, and disseminated HSV infection.

Management of the above adverse events is outlined in **Section 5**.

The maximally tolerated dose (MTD) is the highest dose level below the maximally administered dose when dose escalation decisions are made according to the guidelines above. Enrollment will be stopped when the MTD is determined or the maximally planned dose is acceptably tolerated by six patients.

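### Section 5.1 gives two incompatible triggers, in adjacent sentences, for treating presumed disseminated HSV infection; they conflict for afebrile patients with rash or raised liver tests

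*Combined protocol and SAP*

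**What the plan says.** The bullet on disseminated HSV infection in Section 5.1 contains these elements, in this order.

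- A description of the disease: "In all circumstances, disseminated disease is associated with a systemic host response of fever".
- A first trigger: "Should a patient develop fever, rash, or unexplained elevations in liver function tests in conjunction with a concomitant increase of infectious HSV" in blood by plaque assay, the rise being qualified as "exceeding prior values by 2 logs". The consequence is stated as certain: "patients will undergo a 21 day course of treatment with acyclovir for presumed disseminated HSV infection".
- A second condition, in the next sentence. After noting that viral DNA was found in blood without symptoms in another oncolytic HSV setting, it concludes: "thus, increasing levels as well as fever will both be required to therapeutically intervene".
- An MTD rule, in the sentence after that, under which the earlier level becomes the MTD and enrolment stops: "Should 2 Grade 3 or 4 toxicities attributable to disseminated HSV infection occur in the same dose level, the prior dose level shall be declared".

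Section 4.2 separately lists events that are dose-limiting if likely related to M032. The list ends with "untreatable neurologic deterioration, unresponsive systemic infection, and disseminated HSV infection". It gives no definition or grade for the last item. Section 5.1 also says of its listed events, which include disseminated HSV infection: "Any of the above adverse events will be considered a DLT, if possibly, probably or definitely attributable to M032", subject to a grade condition (Grade 4, or Grade 3 in some situations).

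**The concern.** The first trigger is a sufficient condition: any one of three signs plus the viral rise leads to treatment. The second is a necessary condition: without fever there is no intervention. Where the first is met and the second is not, staff have opposite instructions for a serious infection by a replication-competent study agent. Nothing elsewhere settles it. Section 4.3 allows drugs with anti-HSV activity only for managing an adverse event, which does not say which trigger applies.

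There is a possible second consequence. The documents give no operational case definition of disseminated HSV infection apart from this bullet. Someone deciding whether a patient counts under Section 4.2, or under the two-event MTD rule, may turn to the treatment trigger for want of anything else, and would then meet the contradiction.

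The viral part of the trigger has a gap of its own. It is defined relative to earlier values, and the bullet does not say how to apply it when those values are negative.

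**Working it through.** The plan states no figure to reproduce here; the check is one of logic.

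**Inputs, all from the disseminated-infection bullet in Section 5.1.** Let F = fever, R = rash, L = unexplained raised liver tests, V = the 2-log rise in infectious HSV.

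- First rule: treat if (F or R or L) and V.
- Second rule: treat only if F and V, taking its reference to rising levels to mean the same 2-log rise.

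**Enumeration with V present** (2 × 2 × 2 = 8 combinations):

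| Fever | Rash | Raised liver tests | First rule | Second rule |
|---|---|---|---|---|
| no | no | no | not met | not met |
| no | no | yes | met | **not met** |
| no | yes | no | met | **not met** |
| no | yes | yes | met | **not met** |
| yes | no | no | met | met |
| yes | no | yes | met | met |
| yes | yes | no | met | met |
| yes | yes | yes | met | met |

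The first rule is met in 7 combinations and the second in 4. Every combination that meets the second also meets the first, so they disagree in 7 − 4 = 3: raised liver tests only, rash only, and both, always without fever. With V absent, neither rule is met and they agree.

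**Sensitivity to the assumption on V.** If the second rule meant any increase rather than a 2-log one, the three conflicting combinations would remain, because a 2-log rise is still an increase and fever is still missing. A febrile patient with a smaller rise would not add a conflict: the second rule only states what is required, and the first does not order treatment there.

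**The 2-log criterion with negative earlier samples.** The synopsis and Section 4.1.1 together treat 1 log as a factor of 10, so 2 logs is 10² = 100-fold. With an earlier value p and a new value n, the criterion is log10(n) − log10(p) > 2, or n > 100 × p. If p is recorded as 0, the first form is undefined, while the second becomes n > 0 and any positive sample qualifies. The two ways of writing the same rule then give different answers, and the bullet does not choose between them.

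**Link to DLT and MTD status.** Section 4.2 uses grade and relatedness for non-hematologic toxicity in general, and likely relatedness for the named events. Section 5.1 uses attribution and grade. The MTD rule counts two Grade 3 or 4 toxicities attributable to disseminated HSV infection at one dose level. None of the three refers to fever, the plaque assay or the start of antiviral treatment.

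**The case against.** The best defence is that the second sentence is a parenthetical remark. It explains that viral DNA in blood without symptoms is not enough, so its natural purpose is to require a clinical sign as well as virology. The same bullet says that fever always accompanies disseminated disease and calls such disease exceedingly uncommon, so the conflict concerns a presentation that the protocol does not expect. A reader of one sentence will also see the other.

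This is a fair account of what may have been intended, but it does not remove the contradiction. The second sentence names fever, not clinical signs in general, and says that both elements are required. If fever is taken to be universal, rash and liver tests do no work as alternatives in the first trigger. The protocol does not say which sentence prevails. The point about rarity stands as a limit on how often the conflict would arise.

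A reader might infer more: that the same afebrile patient both is and is not a DLT, and that the MTD turns on which sentence is read. The documents do not support that. The second sentence governs when to intervene, not who is a case. An afebrile patient with a Grade 3 liver-test elevation possibly related to M032 is a DLT under Section 4.2 whichever sentence is followed. One such patient cannot trigger a rule that needs two Grade 3 or 4 toxicities at the same dose level.

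Two further inferences also lack support. Sections 3.1.11 and 4.3 permit steroids but say nothing about their masking fever. No frequency is given for negative earlier blood samples. Nor is a first positive culture ignored: Section 5.1 sends every positive to PCR to separate wild-type virus from M032. For negative earlier samples, the 2-log wording is therefore a point to clarify rather than a contradiction.

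**Conclusion.** The concern holds for the treatment triggers. Section 5.1 contradicts itself for patients with a qualifying viral rise, no fever, and rash, raised liver tests or both: 3 of 8 sign combinations. That count describes logical patterns, not expected patients; the documents give no frequencies from which to estimate how many would be affected. It does not depend on how the second sentence's rising levels are read.

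Carry-over into DLT or MTD counting is a possible consequence of having no separate case definition, not something the text states. Its size cannot be fixed from the documents. Section 4.1.1 assumes cohorts of one, under which a single DLT call could influence the next dose. The synopsis and Section 4.2, however, describe up to three patients per level, and Section 11 describes a three-patient scheme until the first DLT.

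The case for correction rests on the opposite treatment instructions, which are a patient-safety matter in themselves.

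**What to change.** The sponsor, with the Medical Monitor and the DSMB, should reconcile the two sentences in Section 5.1 into one consistent statement of when treatment for presumed disseminated HSV infection is triggered. The same revision should make two things clear:

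1. whether that statement bears on what counts as disseminated HSV infection for the DLT in Section 4.2 and for the two-event MTD rule in Section 5.1, or whether those are judged separately, and if so on what basis;
2. how the 2-log rise is read when earlier samples are negative.

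The choice of trigger and of any threshold belongs to them; this review proposes neither. The cost is a few sentences in Section 5.1, a cross-reference in Section 4.2 if the first item calls for one, and a protocol amendment. No new visit or sample is needed.

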5.2 Dosing Delays/Dose Modifications

Because M032 is delivered as a single dose, there will not be any intra-patient dosing delays or dose modifications.

5.3 Adverse Assessment and Management Assessment by PI/Clinician

Neurologic complications are common in patients with malignant glioma and may be a result of tumor infiltration, mass effect, or other tumor associated complications; radiation administration and its associated direct and indirect toxicities; chemotherapy administration; and other medication and condition-related toxicities. Should 2 or more neurologic toxicities that escalate to the level of a DLT and are not thought to be related to tumor, prior therapy or other treatment associated modalities occur in the same dose level, enrollment will be suspended until an evaluation of these toxicities has been conducted by the trials Data Safety and Monitoring Board (DSMB). The DSMB will be the arbiter as to whether these toxicities can be attributed to M032 and if so, invoke a stopping rule, halting enrollment. If the DSMB should feel that these toxicities are not related to M032 administration, enrollment will be reinstated as per its instructions.

Subjects will be monitored both at UAB and by their referring physician for any treatment-related toxicities until these have resolved back to their pretreatment baseline or < Grade 2.

All unresolved toxicities will be followed regularly by the treating physician and/or research coordinator; the nurse coordinator will conduct follow-up weekly with the subject, family and/or referring physician (by phone if travel is too burdensome for the subject) until resolution of treatment-related toxicity to less than Grade 2 (or Grade 3 if that was the subject's baseline). Additionally, subjects will be monitored monthly for the first 3 months following study drug administration, and will have the nurse-coordinator contact the subject, family and/or referring physician monthly for months 4-6.

6.1 M032 Formulation and Storage

HSV-M032 (NSC 733972), lot # L0909005, is supplied in sterile, labeled 1.0 mL single use glass vials containing 0.5 mL of HSV-M032 suspended in the storage buffer, Dulbecco's Phosphate-buffered Saline (D-PBS), 0.4M NaCl and 10% (w/v) glycerol, pH 7.4. The NExT Program recently reported the 48-month stability assay in which several reserved vials were retested, resulting in a final calculated titer of 3.32×10^9 plaque-forming units PFU/ml or 1.66×10^9 PFU per vial. The vials should remain frozen at -70°C or below until use.

6.2 Availability

M032 will be provided for clinical study under an Agreement between the NIH RAID program and the University of Alabama, Birmingham. For specific shipment information/handling, refer to **Appendix E**.

6.3 Excipient for Dilution of M032

For dilution of M032, a specially formulated excipient solution will be used. This excipient solution (Product Code 103382-50; Lot # 800612) has been purchased from Alanza Inc. ([name]). The formulation is Phosphate Buffered Saline and 10% (w/v) of glycerol, pH 7.0-7.4 and is supplied sterile in 50 ml aliquots in amber serum bottles with snap-cap butyl rubber stoppers.

6.4 M032 Dose Preparation

All matters related to dose preparation and syringe set up for dose administration are performed in a sterile fashion. Prior to beginning infusion, the tubing that is to connect the syringes to the intracranial catheters is primed with sterile PBS + 10% glycerol (Alanza). All of the syringes containing the proper volume of M032 will be prepared at the same time for each three (3) hour period of delivery. Syringes designated to be used beginning at three (3) hours should be kept at 4°C until dispensed to the patient.

To prepare each dose, the vial(s) containing M032 should be thawed by removing it from the controlled access -60°C freezer and rubbing the vial gently between gloved hands until the last ice crystals have melted. The vial should then be placed on ice. Care should be taken to ensure that all the liquid is at the bottom of the vial before removing the cap. If it is suspected that the contents are on the side or top of the vial, the vial can be tapped gently on a flat surface. The cap must be removed carefully to avoid spilling or contamination. The appropriate dose level of M032 will be removed from the vial and diluted in sterile diluent to the total volume. The final diluted M032 should be gently withdrawn into the syringe(s) for infusion.

Once thawed, diluted and maintained at 4°C, the dose must be completely administered to the patient within sixteen hours of preparation. The diluted virus has been shown to be stable at 4°C with no loss of activity for 9 hours.

Complete instructions for dose preparation are described in **Appendices C and D**.

